- Signs, symptoms, or the clinical sequelae of a suspected drug-drug interaction.
- Signs, symptoms, or the clinical sequelae of a suspected overdose of either study intervention or a concomitant medication. Overdose, as a verbatim term (as reported by the investigator), should not be reported as an AE/SAE unless it is an intentional overdose taken with possible suicidal/self-harming intent. Such overdoses should be reported regardless of sequelae and should specify "intentional overdose" as the verbatim term

Events NOT Meeting the AE Definition

- Medical or surgical procedure (eg, endoscopy, appendectomy): the condition that leads to the procedure is the AE.
- Situations in which an untoward medical occurrence did not occur (social and/or convenience admission to a hospital).

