6.1 Serious Adverse Events

DEFINITION OF SAE

If an event is not an AE per definition above, then it cannot be an SAE even if serious conditions are met.

A Serious Adverse Event (SAE) is defined as any untoward medical occurrence that at any dose:

- results in death
- is life-threatening (defined as an event in which the subject was at risk of death at the time of the event; it does not refer to an event which hypothetically might have caused death if it were more severe)
- requires inpatient hospitalization or causes prolongation of existing hospitalization (see **NOTE** below)
- results in persistent or significant disability/incapacity
- is a congenital anomaly/birth defect
- is an important medical event (defined as a medical event(s) that may not be immediately life-threatening or result in death or hospitalization but, based upon appropriate medical and scientific judgment, may jeopardize the subject or may require intervention [eg, medical, surgical] to prevent one of the other serious outcomes listed in the definition above.) Examples of such events include, but are not limited to, intensive treatment in an emergency room or at home for allergic bronchospasm; blood dyscrasias or convulsions that do not result in hospitalization.) Potential drug induced liver injury (DILI) is also considered an important medical event. (See Section 6.6 for the definition of potential DILI.)

Suspected transmission of an infectious agent (eg, pathogenic or nonpathogenic) via the study drug is an SAE.

Pregnancy, Section 6.4, and potential drug induced liver injury (DILI), Section 6.6, must follow the same transmission timing and processes to BMS as used for SAEs. (See Section 6.1.1 for reporting pregnancies).

Any component of a study endpoint that is considered related to study therapy should be reported as SAE (eg, death is an endpoint, if death occurred due to anaphylaxis, anaphylaxis must be reported) (see Section 6.1.1 for reporting details).

NOTE:

The following hospitalizations are not considered SAEs in BMS clinical studies:

- a visit to the emergency room or other hospital department < 24 hours, that does not result
 in admission (unless considered an important medical or life-threatening event)
- elective surgery, planned prior to signing consent
- admissions as per protocol for a planned medical/surgical procedure
- routine health assessment requiring admission for baseline/trending of health status (eg, routine colonoscopy)

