6.1.1 Serious Adverse Event Collection and Reporting

Section 5.6.1 in the nivolumab and ipilimumab IBs presents the Reference Safety Information to determine expectedness of serious adverse events for expedited reporting. Following the subject's written consent to participate in the study, information on all SAEs, whether related or not related to study drug, must be collected, including those thought to be associated with protocol-specified procedures. All SAEs must be collected from the time of signing the consent, including those thought to be associated with protocol-specified procedures and within 100 days of discontinuation of dosing. For subjects randomized/assigned to treatment and never treated with study drug, SAE information should be collected for 30 days from the date of randomization.

The investigator must report any SAE that occurs after these time periods and that is believed to be related to study drug or protocol-specified procedure.

An SAE report must be completed for any event where doubt exists regarding its seriousness.

If the investigator believes that an SAE is not related to study drug, but is potentially related to the conditions of the study (such as withdrawal of previous therapy or a complication of a study procedure), the relationship must be specified in the narrative section of the SAE Report Form.

SAEs, whether related or not related to study drug, and pregnancies must be reported to BMS (or designee) within 24 hours of awareness of the event. SAEs must be recorded on the SAE Report Form; pregnancies on a Pregnancy Surveillance Form (electronic or paper forms). The required method for SAE data reporting collection is through the eCRF. The paper SAE/pregnancy surveillance forms are only intended as a back-up option when the eCRF system is not functioning. When paper forms are used, the original paper forms are to remain on site. In this case, the paper forms are to be transmitted via email or confirmed facsimile (fax) transmission to:

SAE Email Address: Refer to Contact Information list.

SAE Facsimile Number: Refer to Contact Information list.

For studies capturing SAEs through electronic data capture (EDC), electronic submission is the required method for reporting. In the event the electronic system is unavailable for transmission, paper forms must be used and submitted immediately. When paper forms are used, the original paper forms are to remain on site.

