6.5 Overdose

All occurrences of overdose must be reported as SAEs (see Section 6.1.1 for reporting details).

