#### 7.1.1 ***Adverse Events, Serious Adverse Events, Multiple Events, Select Adverse Events, Other Events of Special Interest and Immune-Mediated Adverse Events***

Drug-related AEs are those events with relationship to study drug “Related”, as recorded on the CRF. If the relationship to study drug is missing, the AE will be considered as drug-related.

Serious adverse events consist of AEs deemed serious by the Investigator and flagged accordingly in the CRF and clinical database.

Adverse events leading to study drug discontinuation are AEs with action taken regarding study drug(s) = “Drug was discontinued”.

Adverse events leading to dose delay are AEs with action taken regarding study drug(s) = “Drug was delayed”.

Adverse events leading to dose reduction are AEs with action taken regarding study drug(s) = “Dose was reduced”.

Adverse events will be coded using the Medical Dictionary for Regulatory Activities (MedDRA), and the most recent version of the dictionary at the time of the database lock will be used. Adverse events results will be graded for severity using NCI Common Terminology Criteria for Adverse Events (CTCAE) and the most recent version of the criteria at the time of the database lock will be used.

In the AE summary tables, unless otherwise specified, subjects will be counted only once at the Preferred Term (PT), only once at the System Organ Class (SOC), and only once at subject level for the counting of total number of subjects with an AE. The AE tables will be sorted by the SOCs and then PTs. SOC will be ordered by descending frequency overall and then alphabetically. PTs will be ordered within SOC by descending frequency overall and then alphabetically. The sorting will be done based on the ‘Any Grade’ column of the experimental arm when arms are presented side-by-side.

Unless otherwise specified, the AE summary tables will be restricted to on-treatment events regardless of the causality.

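### Protocol Sections 6, 6.1 and 6.5 give opposite SAE-reporting instructions for an unintentional overdose with no sequelae or only non-serious ones

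*Protocol*

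**What the plan says.** Four parts of the protocol and one of the SAP bear on this.

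- **Protocol Section 6, list of events that meet the AE definition.** What counts as an AE is "Signs, symptoms, or the clinical sequelae of a suspected overdose of either study intervention or a concomitant medication". The overdose itself is handled separately: as the term the investigator records, it "should not be reported as an AE/SAE unless it is an intentional overdose taken with possible suicidal/self-harming intent". For that exception, "Such overdoses should be reported regardless of sequelae".
- **Protocol Section 6.1.** "If an event is not an AE per definition above, then it cannot be an SAE even if serious conditions are met".
- **Protocol Section 6.5.** "All occurrences of overdose must be reported as SAEs". The section refers to Section 6.1.1 for the details and makes no exception for intent or sequelae.
- **Protocol Section 6.1.1.** SAEs "must be reported to BMS (or designee) within 24 hours of awareness of the event".
- **SAP Section 7.1.1.** "Serious adverse events consist of AEs deemed serious by the Investigator and flagged accordingly in the CRF and clinical database". SAP Section 7.6.2 then tabulates SAEs by treatment group.

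**The concern.** Sections 6 and 6.5 both address overdose directly and both are current text. One tells the site not to report an unintentional overdose under that term as an AE or SAE. The other tells the site to report every overdose as an SAE. A site that follows Section 6 sends no expedited report for an accidental overdose without sequelae; a site that follows Section 6.5 sends one within 24 hours.

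Two things are at stake. The first is consistent expedited safety reporting across sites. The second is what the SAE tables mean: they are built from the investigator's seriousness flag, and the SAP sections cited contain no step that would bring overdose reports to a common convention.

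**Working it through.** No arithmetic applies. The check is to take each kind of overdose through both rules.

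| Case | Under Sections 6 and 6.1 | Under Section 6.5 | Result |
|---|---|---|---|
| Intentional, possible self-harm intent | Reportable, with or without sequelae | SAE | No conflict over reporting |
| Unintentional, no sequelae | Nothing to report; not an AE, so cannot be an SAE | SAE, 24-hour report | Direct conflict |
| Unintentional, non-serious sequelae | Non-serious AE under the sequela term | SAE for the overdose, 24-hour report | Conflict on seriousness and on term |
| Unintentional, serious sequelae | SAE under the sequela term | SAE | SAE report due either way; only the term is in doubt |

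Three further checks:

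1. **Does Section 6.1 offer a bridge?** It says that pregnancy and potential drug-induced liver injury follow the SAE timing and process. It says nothing of the kind for overdose. Its opening rule, that a non-AE cannot be an SAE, makes the second row sharper: the event is excluded under Section 6.1 and required under Section 6.5.
2. **Does either rule take precedence?** Neither the protocol nor the SAP says so. Section 6.5 is the dedicated overdose section, but Section 6 names overdose just as specifically and covers both AEs and SAEs. The protocol does not define overdose.
3. **Does the analysis settle it?** No. An overdose that a site flags as serious enters the SAE tables, and one that a site does not report is absent from them.

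**The case against.** **The Section 6 sentence is softer and narrower than a prohibition.** It says should not, it governs overdose as a verbatim term, and its exception is limited to possible suicidal or self-harming intent. A site could satisfy it by reporting the sequela instead. This works when the sequela is serious. It fails when there is no sequela to report, and when the sequela is non-serious, because Section 6.5 still requires an SAE.

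**Section 6.1.1 asks for an SAE report whenever seriousness is in doubt.** This pushes an uncertain site towards reporting, most clearly when there are non-serious sequelae. It does not decide whether an overdose without sequelae is an AE at all, so it does not remove the conflict.

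**A reader might infer that safety signals from dosing errors would be missed.** The documents do not support that. Sequelae are AEs under Section 6 whichever overdose rule a site follows. Dosing is also recorded independently: SAP Section 7.4.1 calls for cumulative dose, relative dose intensity with a category of 110% or more, and a by-subject dosing listing. A single overdose may not shift overall intensity, but the dosing record does not depend on the AE rule.

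**A reader might also infer that SAE counts by arm are distorted.** That is not shown. The inconsistency acts through sites, and a site's reading of the rule would apply to all arms there. In the primary comparison both arms receive the same chemotherapy doses and schedules. The nivolumab-plus-ipilimumab arm receives no chemotherapy, so an uneven effect there is conceivable, but the documents give no evidence of one. Nor do they support singling out capecitabine or infusional fluorouracil as the likely source of overdoses.

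**The CRF completion guidelines might already settle the matter.** Protocol Section 9.2.3 mentions them, but they are not among the documents reviewed, so this cannot be judged. Even if they do, the protocol text would still contradict itself.

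**Conclusion.** The inconsistency is real, but limited to unintentional overdoses with no sequelae or only non-serious ones. For these, no site can follow Sections 6, 6.1 and 6.5 together. It would be too strong to say that every unintentional overdose is affected: with serious sequelae an SAE report is due under either rule.

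The consequence is possible variation between sites in 24-hour reporting and in absolute SAE counts. Its size cannot be given, because the documents state no number of overdoses and no breakdown by intent or sequelae. Efficacy results, alpha, sample size and power do not depend on it. The conclusion assumes that no separate study instruction already tells sites which rule to follow. The point is an internal inconsistency, not a design choice, and it is worth correcting because it concerns an operative safety-reporting rule. This review takes no position on which rule should prevail.

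**What to change.** 1. **Protocol.** Reconcile Sections 6, 6.1 and 6.5 into one overdose-reporting rule. It should state what counts as an overdose, whether intent or sequelae change the reporting duty, under which term the event is recorded, and whether the 24-hour timeline applies. If overdose is to follow SAE timing without being an AE, Section 6.1 needs to say so, as it does for pregnancy.
2. **CRF completion guidelines.** Check that they match the agreed rule, and amend them if they do not.
3. **Data already collected.** Query overdose reports so that the SAE tables use one convention. The by-subject dosing listing in SAP Section 7.4.1 can help to find overdoses that were never reported as events, once the sponsor has defined the term. Accrual ended in May 2019, so this step matters as much as the new wording.

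The cost is an administrative letter or a short amendment, plus a small data query. No planned efficacy analysis changes.

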6.1 Serious Adverse Events

DEFINITION OF SAE

If an event is not an AE per definition above, then it cannot be an SAE even if serious conditions are met.

A Serious Adverse Event (SAE) is defined as any untoward medical occurrence that at any dose:

- results in death
- is life-threatening (defined as an event in which the subject was at risk of death at the time of the event; it does not refer to an event which hypothetically might have caused death if it were more severe)
- requires inpatient hospitalization or causes prolongation of existing hospitalization (see **NOTE** below)
- results in persistent or significant disability/incapacity
- is a congenital anomaly/birth defect
- is an important medical event (defined as a medical event(s) that may not be immediately life-threatening or result in death or hospitalization but, based upon appropriate medical and scientific judgment, may jeopardize the subject or may require intervention [eg, medical, surgical] to prevent one of the other serious outcomes listed in the definition above.) Examples of such events include, but are not limited to, intensive treatment in an emergency room or at home for allergic bronchospasm; blood dyscrasias or convulsions that do not result in hospitalization.) Potential drug induced liver injury (DILI) is also considered an important medical event. (See Section 6.6 for the definition of potential DILI.)

Suspected transmission of an infectious agent (eg, pathogenic or nonpathogenic) via the study drug is an SAE.

Pregnancy, Section 6.4, and potential drug induced liver injury (DILI), Section 6.6, must follow the same transmission timing and processes to BMS as used for SAEs. (See Section 6.1.1 for reporting pregnancies).

Any component of a study endpoint that is considered related to study therapy should be reported as SAE (eg, death is an endpoint, if death occurred due to anaphylaxis, anaphylaxis must be reported) (see Section 6.1.1 for reporting details).

NOTE:

The following hospitalizations are not considered SAEs in BMS clinical studies:

- a visit to the emergency room or other hospital department < 24 hours, that does not result
 in admission (unless considered an important medical or life-threatening event)
- elective surgery, planned prior to signing consent
- admissions as per protocol for a planned medical/surgical procedure
- routine health assessment requiring admission for baseline/trending of health status (eg, routine colonoscopy)
- medical/surgical admission other than to remedy ill health and planned prior to entry into the study. Appropriate documentation is required in these cases

 admission encountered for another life circumstance that carries no bearing on health status and requires no medical/surgical intervention (eg, lack of housing, economic inadequacy, caregiver respite, family circumstances, administrative reason)

 Admission for administration of anticancer therapy in the absence of any other SAEs (applies to oncology protocols).

EVALUATING AES AND SAES

Assessment of Causality

- The investigator is obligated to assess the relationship between study intervention and each occurrence of each AE/SAE.
- A "reasonable possibility" of a relationship conveys that there are facts, evidence, and/or arguments to suggest a causal relationship, rather than a relationship cannot be ruled out.
- The investigator will use clinical judgment to determine the relationship.
- Alternative causes, such as underlying disease(s), concomitant therapy, and other risk factors, as well as the temporal relationship of the event to study intervention administration will be considered and investigated.
- The investigator will also consult the Investigator's Brochure (IB) and/or Product Information, for marketed products, in his/her assessment.
- For each AE/SAE, the investigator must document in the medical notes that he/she has reviewed the AE/SAE and has provided an assessment of causality.
- There may be situations in which an SAE has occurred and the investigator has minimal information to include in the initial report to Sponsor. However, it is very important that the investigator always make an assessment of causality for every event before the initial transmission of the SAE data to Sponsor.
- The investigator may change his/her opinion of causality in light of follow-up information and send a SAE follow-up report with the updated causality assessment.
- The causality assessment is one of the criteria used when determining regulatory reporting requirements.

6.1.1 Serious Adverse Event Collection and Reporting

Section 5.6.1 in the nivolumab and ipilimumab IBs presents the Reference Safety Information to determine expectedness of serious adverse events for expedited reporting. Following the subject's written consent to participate in the study, information on all SAEs, whether related or not related to study drug, must be collected, including those thought to be associated with protocol-specified procedures. All SAEs must be collected from the time of signing the consent, including those thought to be associated with protocol-specified procedures and within 100 days of discontinuation of dosing. For subjects randomized/assigned to treatment and never treated with study drug, SAE information should be collected for 30 days from the date of randomization.

The investigator must report any SAE that occurs after these time periods and that is believed to be related to study drug or protocol-specified procedure.

An SAE report must be completed for any event where doubt exists regarding its seriousness.

If the investigator believes that an SAE is not related to study drug, but is potentially related to the conditions of the study (such as withdrawal of previous therapy or a complication of a study procedure), the relationship must be specified in the narrative section of the SAE Report Form.

SAEs, whether related or not related to study drug, and pregnancies must be reported to BMS (or designee) within 24 hours of awareness of the event. SAEs must be recorded on the SAE Report Form; pregnancies on a Pregnancy Surveillance Form (electronic or paper forms). The required method for SAE data reporting collection is through the eCRF. The paper SAE/pregnancy surveillance forms are only intended as a back-up option when the eCRF system is not functioning. When paper forms are used, the original paper forms are to remain on site. In this case, the paper forms are to be transmitted via email or confirmed facsimile (fax) transmission to:

SAE Email Address: Refer to Contact Information list.

SAE Facsimile Number: Refer to Contact Information list.

For studies capturing SAEs through electronic data capture (EDC), electronic submission is the required method for reporting. In the event the electronic system is unavailable for transmission, paper forms must be used and submitted immediately. When paper forms are used, the original paper forms are to remain on site.

SAE Telephone Contact (required for SAE and pregnancy reporting): Refer to Contact Information list.

Follow-up of AEs and SAEs

If only limited information is initially available, follow-up reports are required. (Note: Follow-up SAE reports must include the same investigator term(s) initially reported.)

If an ongoing SAE changes in its intensity or relationship to study drug or if new information becomes available, the SAE report must be updated and submitted within 24 hours to BMS (or designee) using the same procedure used for transmitting the initial SAE report.

All SAEs must be followed to resolution or stabilization.

BMS will be reporting adverse events to regulatory authorities and ethics committees according to local applicable laws including European Directive 2001/20/EC and FDA Code of Federal Regulations 21 CFR Parts 312 and 320. A SUSAR (Suspected, Unexpected Serious Adverse Reaction) is a subset of SAEs and will be reported to the appropriate regulatory authorities and investigators following local and global guidelines and requirements.

6.2 Nonserious Adverse Events

A *nonserious adverse event* is an AE not classified as serious.

6.2.1 Nonserious Adverse Event Collection and Reporting

The collection of nonserious AE information should begin at initiation of study drug. Nonserious AE information should also be collected from the start of a placebo lead-in period or other observational period intended to establish a baseline status for the subjects.

Nonserious AEs should be followed to resolution or stabilization, or reported as SAEs if they become serious (see Section 6.1.1). Follow-up is also required for nonserious AEs that cause interruption or discontinuation of study drug and for those present at the end of study treatment as appropriate. All identified nonserious AEs must be recorded and described on the nonserious AE page of the CRF (paper or electronic).

Completion of supplemental CRFs may be requested for AEs and/or laboratory abnormalities that are reported/identified during the course of the study.

Information on all nonserious adverse events (not only those deemed to be treatment-related) should be collected continuously during the treatment period and for a minimum of 100 days following discontinuation of study treatment.

Every adverse event must be assessed by the investigator with regard to whether it is considered immune-mediated. For events which are potentially immune-mediated, additional information will be collected on the subject's case report form.

